6.3. Secondary Efficacy Endpoints and Analysis

6.3.1. Secondary Endpoints

The secondary efficacy endpoints are presented in Section 1.1. The response and remission secondary endpoints at Week 14 are presented in Table 4 and Table 5.

6.3.1.1. Secondary Endpoints Analysis

All secondary efficacy endpoints will be analyzed separately for UC and CD participants.

All binary secondary efficacy endpoints (response/remission/improvement at week 14 and clinical response based on CDAI at weeks 4, 8, and 12) will be analyzed using the following methods:

1. Beta-Binomial model with non-informative Beta (1,1) prior, as described in Section 6.2.2.
2. Logistic regression model as described in Section 6.2.3.
3. Cochran-Mantel-Haenszel (CMH) test for pairwise comparisons between the active dose groups and placebo separately for UC and CD, as described in Section 6.2.3.
4. Cochran-Mantel-Haenszel (CMH) test for pairwise comparisons between the active dose groups and placebo separately for UC and CD, stratified by actual previous exposure to advanced IBD therapy (yes/no), as described in Section 6.2.3. The model will be used if data permits.

For the Bayesian analysis, the posterior means of the response rates, two-sided 95% credible intervals for difference in response rates, and the posterior probability that (TEV-48574 response rate – placebo response rate > 0) will be reported.

For the frequentist analyses (logistic regression and CMH), the odds ratios, difference in response rates, and the associated two-sided 95% confidence intervals (CIs) and nominal one-sided- p-values will be reported.

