	
 Clinical remission defined as score of rectal bleeding = 0 and stool frequency = 0 on the PRO2-UC scale at week 14 
The secondary efficacy endpoints to be measured in participants with moderate to severe CD are as follows:
 
 Clinical response defined as a ≥ 100-point decrease in Crohn's Disease Activity Index (CDAI) score from baseline at weeks 4, 8, 12 and 14 Clinical remission defined as a CDAI score < 150 at week 14 Clinical response defined as a decrease from baseline of at least 50% in PRO2 (PRO2-CD; abdominal pain and stool frequency) at week 14 Clinical remission defined as abdominal pain ≤ 1 and stool frequency ≤ 3 on the PRO2 scale at week 14 Endoscopic response defined as a decrease in modified multiplier (MM)-SES-CD of $> 50\%$ from baseline at week 14

A secondary objective of the trial is to evaluate the safety and tolerability of 3 different dose regimens of TEV-48574 sc administered Q2W in adult participants with IBD (moderate to severe UC or CD).
	
The safety and tolerability measures/parameters are as follows:
 
 Adverse events Change from baseline in clinical laboratory test results (serum chemistry, hematology, and urinalysis) Change from baseline in vital signs measurements (blood pressure, pulse rate, body temperature, and respiratory rate) Change from baseline in 12-lead electrocardiogram findings Participants who stopped the investigational medicinal product due to adverse events Local tolerability at the injection site

A secondary objective of the trial is to evaluate the immunogenicity of 3 different dose regimens of TEV-48574 sc administered Q2W in adult participants with IBD (moderate to severe UC or CD).
	
The immunogenicity endpoints for this trial are as follows:
 
 Treatment-emergent anti-drug antibody (ADA) at weeks 2, 4, 8, 14, and follow-up visit

Objectives	Endpoints
	
• Presence of neutralizing ADA in ADA positive participants at weeks 2, 4, 8, 14, and follow-up visit

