2.2. Randomization and Blinding

This is a randomized, double-blind, placebo-controlled trial. Participants who meet all the inclusion criteria and none of the exclusion criteria will be randomly assigned to the 3 treatment arms: TEV-48574 900mg Q2W, TEV-48574 450mg Q2W or placebo in a 1:1:1 ratio, stratified by indication (UC or CD) and previous exposure to advanced therapy for IBD (yes/no) (biologics, JAK inhibitors, and S1P receptor modulators).

Table 1: Treatment Arms

Treatment Arm	Treatment (Q2W)
TEV-48574 900mg Q2W	TEV-48574 2250 mg (single loading dose)/900 mg (6 induction doses)
TEV-48574 450mg Q2W	TEV-48574 2250 mg (single loading dose)/450 mg (6 induction doses)
Placebo	Placebo

Q2W=every 2 weeks

Participants randomized prior to Amendment 03 with Revision 01 were randomized in a 1:1:1:1 ratio to TEV-48574 1800mg Q2W, TEV-48574 900mg Q2W, TEV-48574 450mg Q2W or placebo.

Participants will be randomly assigned to the treatment groups by means of a computer-generated randomization list using interactive-response technology.

Personnel who may be aware of IMP assignments will not be involved in the conduct of any trial procedures or assessment of any adverse events.

The participants, site, and sponsor trial team will be blinded until all participants complete the trial, and the database is locked for final analysis.

Pharmacokinetic, pharmacodynamics and immunogenicity samples will be collected for bioanalysis during the trial. Individuals responsible for sample bioanalysis and other responsible personnel may know who received test IMP and who received placebo IMP during the trial. Personnel responsible for bioanalysis will be provided with the randomization code to facilitate the analysis. However, the personnel responsible for bioanalysis will not have access to clinical safety and efficacy data and will provide concentration data to other personnel in a manner that will not identify individual participants (i.e., a dummy participant identifier will be linked to the concentration data of an individual participant).

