Endoscopic response 2 (SES-CD)	$> 50\%$ decrease in SES-CD from baseline, or a decrease of at least 2 points for subjects with a baseline score of 4 and isolated ileal disease	Supplementary to primary
Endoscopic response (MM-SES-CD)	$\geq 50\%$ decrease in MM-SES-CD from baseline	Secondary
Clinical response (CDAI)	≥ 100 -point decrease in CDAI score from baseline	Secondary
Clinical remission (CDAI)	CDAI score < 150	Secondary
Clinical response (PRO2)	$\geq 50\%$ decrease in PRO2 from baseline	Secondary
Clinical response 2 (PRO2)	$\geq 30\%$ decrease in PRO2 from baseline	Exploratory
Clinical remission (PRO2)	abdominal pain ≤ 1 , and stool frequency ≤ 3	Secondary
Clinical remission 2 (PRO2)	abdominal pain ≤ 1 , and stool frequency ≤ 1.5	Exploratory
Clinical remission 3 (PRO2)	abdominal pain ≤ 1 , and stool frequency ≤ 2.8	Exploratory
Endoscopic remission (SES-CD)	SES-CD score of 0-2	Exploratory
Endoscopic remission 2 (SES-CD)	SES-CD score of 0-4 with no individual subscore > 1	Exploratory
Histologic response (GHA)	$\geq 50\%$ decrease in GHA Score from baseline	Exploratory

Similar secondary/exploratory response and remission endpoints based on PRO2 and CDAI are defined at all timepoints where they are assessed. Details regarding the CDAI and PRO2-CD scores are provided in [Appendix 4](#) and [Appendix 5](#).

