6.2.3. Sensitivity and Supplementary Analysis

The following sensitivity and supplementary analyses of the primary endpoint will be performed:

1. Tipping point analysis will be performed to test the robustness of the primary analysis conclusion to the non-response imputation of participants that discontinue the trial or have missing week 14 MMS (UC participant) or SES-CD (CD participants) data used in the primary analysis. The tipping point analysis will be conducted by varying the number of participants imputed as non-responders in the active and placebo groups.
2. A supplementary analysis for the primary endpoint using the response variables defined in the first supplementary estimand, clinical remission 2 (MMS) for UC and endoscopic response2 (SES-CD) for CD (see [Table 5](#)), will be performed. The primary analysis model will be used in this analysis.
3. A supplementary analysis for the primary efficacy variable will be performed using a logistic regression model fit separately to each indication with the following fixed effects: dose (as categorical variable), actual previous exposure to advanced IBD therapy (yes/no), and baseline MMS (UC participants) or SES-CD (CD participants).
 - Each comparison of TEV-48574 dose versus placebo will be tested (one-sided-) at a nominal significance level of $\alpha=0.1$.
 - Odds ratios (for each of the TEV-48574 doses versus placebo), associated two-sided 95% confidence intervals (CIs), and nominal one-sided- p-values will be reported.
4. Cochran-Mantel-Haenszel (CMH) test for pairwise comparisons between the active dose groups and placebo separately for UC and CD. Odds ratios (for each of the TEV-48574 doses versus placebo), difference in response rate, and the associated two-sided 95% CIs and nominal one-sided- p-values will be reported.
5. Cochran-Mantel-Haenszel (CMH) test for pairwise comparisons between the active dose groups and placebo separately for UC and CD, stratified by actual previous exposure to advanced IBD therapy (yes/no). The model will be used if data permits. Odds ratios (for each of the TEV-48574 doses versus placebo), difference in response rates, and the associated two-sided 95% CIs and nominal one-sided- p-values will be reported.

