APPENDIX 5. PRO2-CD SCORE

Table 18: Definition of PRO2-CD Score

Score	Data	Derivation
PRO2-CD Stool Frequency Subscore	Mean number of liquid or soft stools in 7-day period	Mean value <0.5 → subscore=0; Mean value ≥ 0.5 and < 1.5 → subscore =1; Mean value ≥ 1.5 and < 2.5 → subscore = 2; Mean value ≥ 2.5 → subscore =3
PRO2-CD Abdominal Pain Subscore	Mean abdominal pain in 7-day period	
PRO2-CD Score	Sum of stool frequency and abdominal pain subscores	

Derivation of PRO2-CD Score:

- Calculate the stool frequency and abdominal pain mean values at: derived baseline, weeks 2 to 12, and week 14 using the rules as described in [Appendix 4](#) for CDAI.
- Derive the subscores (range 0-3) as described in [Table 18](#).
- PRO2-CD is the sum of the stool frequency and abdominal pain subscores.

Note that the binary efficacy endpoints based on PRO2-CD (see [Table 5](#)) use cutoffs for the mean values and not the subscores.

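### The logistic model for the Crohn's symptom endpoints (CDAI, PRO2-CD) adjusts for baseline SES-CD, so chance imbalance in baseline symptoms is left largely uncorrected

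*SAP*

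**What the plan says.** Section 6.3.1.1 lists four methods for the binary secondary endpoints, which it describes as "response/remission/improvement at week 14 and clinical response based on CDAI at weeks 4, 8, and 12". Item 2 is the "Logistic regression model as described in Section 6.2.3".

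Section 6.2.3 item 3 defines that model, fitted per indication, with dose as a categorical term, "actual previous exposure to advanced IBD therapy (yes/no), and baseline MMS (UC participants) or SES-CD (CD participants". Section 6.3.1.1 does not replace any term. Where the SAP wants the model altered, it says so: Section 6.2.4 drops previous advanced therapy for the subgroup analysis on that factor. The literal reading of 6.3.1.1 is therefore the fair one.

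Four of the five Crohn's secondary definitions in Section 1.1 are symptom-based: CDAI response, CDAI remission, PRO2-CD response and PRO2-CD remission. CDAI remission is an absolute cut: "Clinical remission defined as a CDAI score < 150 at week 14". PRO2-CD has no endoscopic part: "PRO2-CD is the sum of the stool frequency and abdominal pain subscores".

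Randomization (Section 2.2) is "stratified by indication (UC or CD) and previous exposure to advanced therapy for IBD (yes/no"), with no symptom score.

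**The concern.** A baseline covariate earns its place by predicting the outcome and by absorbing chance differences between arms in that predictor. SES-CD does this naturally for the primary endpoint. For a symptom endpoint the obvious predictor is the starting symptom score, above all when the endpoint is an absolute cut such as "CDAI score < 150": a participant who enters nearer to the threshold has less far to go.

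The logistic model is the only secondary method that contains a baseline severity score. The Beta-binomial model and the unstratified CMH test have no covariate, and the other CMH test is stratified only by previous advanced therapy. As written, no secondary analysis adjusts for baseline CDAI or PRO2-CD. If one arm starts with milder symptoms by chance, all four results lean the same way. The adjusted odds ratio, which a reader would expect to correct for this, largely does not.

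**Working it through.** **The plan's own figures.** The SAP gives no operating characteristics for the secondary logistic model. Table 3 (Beta-binomial, 40 per arm, cutoff 0.90) reproduces by exact enumeration: null 7.87% (UC) and 9.56% (CD), efficacy 91.0% and 87.2%. That confirms the design inputs but does not bear on the covariate.

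**Inputs from the SAP.** 40 per arm (Section 2.5); one-sided nominal level 0.10 and the model terms (Section 6.2.3).

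**Assumed inputs, not in the SAP.** Correlation r between SES-CD and CDAI: 0, 0.2, 0.4. Correlation ρ between baseline and week-14 CDAI: 0.3 to 0.5 (0.6 shown once). Baseline CDAI about 310 (SD 60, range 220-450); week-14 SD 100.

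**Step 1: size of chance imbalance.** The difference in baseline means between two arms has SD √(2/40) = 0.224 baseline SDs. The chance that one named arm starts more than 0.25 SD lower is Φ(−0.25/0.224), about 13%.

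**Step 2: how much SES-CD removes.** In a linear approximation, adjusting for a covariate correlated r with CDAI leaves the fraction 1 − r² of the shift caused by a CDAI imbalance: 1.00, 0.96 and 0.84 for r = 0, 0.2 and 0.4. Most of it stays.

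**Step 3: effect on the CDAI remission difference.** The normal density at the cut is about 0.0029 per CDAI point. A 1-SE imbalance with ρ = 0.5 moves the difference by 0.5 × 0.224 × 100 × 0.0029 = 0.032, about 3 percentage points. A 2-SE imbalance moves it about 6. At r = 0.2 this is multiplied by 0.96.

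**Step 4: simulation of the model.** Three arms of 40, about 4,000 trials per setting. The model contains dose, previous advanced therapy and one baseline score. The assumed log-odds of the endpoint are 0.5 or 1.0 per SD lower baseline CDAI; the treatment log-odds are 0 or 1.0; r is 0, 0.2 or 0.4.

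| Quantity | SES-CD covariate | Own baseline (CDAI) |
|---|---|---|
| Size of shift in log-odds ratio per 1 SD CDAI imbalance | 0.40 to 0.95 | about 0 (at most 0.05) |
| False-positive rate, all trials | 9-11% | 9-11% |
| False-positive rate when the high-dose arm starts >0.25 SD lower (about 13% of trials) | 17-23% | 8-11% |
| Power, all trials | 66-72% | 71-73% |

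**Step 5: power by endpoint.** 40 v 40, week-14 CDAI linear in baseline, r = 0.2. For CDAI remission, SES-CD against own baseline:
- ρ = 0.3: 71.7% v 73.3%, a gain of 1.6 points
- ρ = 0.5: 71.6% v 76.3%, a gain of 4.7 points
- ρ = 0.6: 72.1% v 79.0%, a gain of 6.9 points

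With r varied over 0 to 0.4, the gain is about 1-2 points at ρ = 0.3 and up to about 5 at ρ = 0.5.

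For CDAI 100-point response the gain is about 1 point or none. The endpoint is a change score, and the slope of change on baseline is ρ × 100/60 − 1, which is −0.50, −0.17 and 0 at ρ = 0.3, 0.5 and 0.6. As ρ rises towards 0.6, baseline stops predicting the change. PRO2-CD was not simulated.

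**The case against.** The strongest reply is that this is a matter of efficiency and not an error. SES-CD is a legitimate prespecified covariate, and the average false-positive rate is the same with either choice. The logistic model is one of four methods; its p-values are nominal; Section 7 makes no multiplicity adjustment; and the success rule in Section 6.2.2 concerns only the primary endpoint. A shift of 3 points is about a third of the standard error of a 40 v 40 difference: √(0.12 × 0.88/40 + 0.34 × 0.66/40) = 9.1 points at the SAP's planning rates. Baseline CDAI and PRO2-CD are tabulated by arm (Sections 5.1 and 5.4), so an imbalance would be visible.

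All of that stands, and it limits the point to a minor one. It does not remove it. Seeing an imbalance in a table does not correct the estimate, and choosing the covariate after unblinding would be open to challenge.

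Three stronger readings are tempting, and the documents do not support them:
- That the type I error is inflated. The excess appears only in trials with an unfavourable imbalance and averages out over all trials.
- That all four symptom endpoints lose power alike. The argument from an absolute cut covers the two remission endpoints. The response endpoints are defined relative to baseline, and CDAI response hardly changes.
- That ulcerative colitis is affected in the same way. MMS already contains rectal bleeding and stool frequency, the two PRO2-UC items.

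It would also be wrong to treat the change as free. CDAI is missing if any of its eight items is missing, and the diary items need a minimum number of entries (Section 4.3.2, Appendix 4). A participant without a baseline CDAI can still be classified for CDAI remission, but would drop out of a model that requires that baseline.

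**Conclusion.** The point holds as a minor one. By cross-reference, the Crohn's symptom endpoints are adjusted for an endoscopic baseline, and chance imbalance in baseline symptoms is left largely uncorrected. I say largely because SES-CD removes a share that depends on its correlation with CDAI, which the SAP does not give; at an assumed 0.4 that share is about 16%.

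The consequence is conditional bias when baselines differ, and a power loss of about 1-5 points for CDAI remission at ρ = 0.3-0.5. For PRO2-CD remission the same direction is expected by reasoning alone. All sizes rest on the assumed inputs above. The primary analysis and its success rule are untouched.

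**What to change.** In Section 6.3.1.1 item 2, add for Crohn's disease that the baseline covariate is baseline CDAI for the CDAI endpoints and the baseline PRO2-CD item means (stool frequency, abdominal pain) for the PRO2-CD endpoints. Keep previous advanced therapy in the model. Leave the UC model with MMS as it is. Using baseline MM-SES-CD for the MM-SES-CD endpoint is optional, since SES-CD is close to it.

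Two clarifications belong with this:
- Name the baseline CDAI. Section 4.2.1 limits the derived baseline CDAI to sensitivity analysis, so the covariate must be another stated baseline value, or that sentence must be amended.
- State how a missing baseline score is handled so that no participant leaves the model, for example by imputing the overall baseline mean for the covariate only.

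The cost is a few sentences and one changed model term, made before database lock. The scores are already collected and summarised. The only downside is the handling rule for the few missing baseline diary scores.

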6.4. Exploratory Efficacy Endpoints and Analysis

The exploratory efficacy endpoints are presented in Section 1.3. The response and remission exploratory endpoints at Week 14 are presented in Table 4 and Table 5.

Binary endpoints will be summarized using descriptive statistics for categorical data. In addition, a graph of response rate at each visit will be presented where applicable.

Summary statistics for PRO2-UC items, PRO2-UC total score, PRO2-CD items, PRO2-CD total score, and CDAI score will be presented by visit. Actual values and changes from baseline to each visit will be provided. In addition, graphs of mean change from baseline to each visit by treatment group will be presented.

6.4.1. Efficacy Biomarkers

The following efficacy biomarkers endpoints will be summarized as part of the statistical analysis of exploratory efficacy endpoints:

- hsCRP:
 - hsCRP change from baseline at each visit
 - hsCRP percent change from baseline at each visit
 - hsCRP <5 mg/L, hsCRP ≥ 5 mg/L at each visit
- fecal calprotectin:
 - fecal calprotectin change from baseline at each visit
 - fecal calprotectin percent change from baseline at each visit
 - fecal calprotectin ≤ 250 mg/kg, fecal calprotectin > 250 mg/kg at each visit

- albumin:
 - albumin change from baseline at each visit
 - Albumin percent change from baseline at each visit
 - albumin ≤ 35 g/L, albumin > 35 g/L at each visit

Summary statistics for hsCRP fecal calprotectin, and albumin will be presented by visit. Actual values, change from baseline, and percent change from baseline to each visit will be provided. In addition, graphs of median value, median change from baseline and median percent change from baseline to each visit by treatment group will be presented. Box plots of hsCRP, fecal calprotectin, and albumin will be presented.

The analysis will be repeated by response at week 14 (yes/no) as defined by the primary endpoint.

7. MULTIPLE COMPARISONS AND MULTIPLICITY

No adjustments to control the false-positive rate will be made for the preplanned multiple comparisons/endpoints analyses in this phase II study.

8. SAFETY ANALYSIS

8.1. General

The safety analysis set will be used for all safety analyses. Summaries will be presented by treatment and pooled TEV-45874, separately by indication (UC or CD) and pooled (UC and CD). The summaries will include participants in the 1800 mg treatment group that were randomized prior to PA03Rev01.

If an indication is stopped for safety reasons (see Section 13.1), pooled analyses of UC and CD will not be presented.

Safety listings will include all data collected, starting from screening. Safety summary tables will include all treatment-emergent data, ie, data collected from first day of trial drug until the end of the trial (including the FU period), unless specified otherwise.

8.2. Duration of Exposure to Trial and Trial Drug

Duration of trial (days in trial) is the number of days starting from Day 1 to the last visit day in the trial (last visit day – Day 1 + 1).

Duration of exposure is the number of days starting from the 1st day of trial drug to 4 weeks after last dosing (4 weeks after last dosing – first day of trial drug + 1).

Number of doses received (planned dose schedule is 1 loading dose and 6 induction doses) will be summarized as categorical data using descriptive statistics.

Weeks on treatment will be summarized as categorical data using the categories ≥ 2 weeks, ≥ 4 weeks, ≥ 6 weeks, ≥ 8 weeks, ≥ 10 weeks, and ≥ 12 weeks using descriptive statistics. Duration of treatment (days) will also be summarized as continuous data using descriptive statistics.

8.3. Adverse Events

All adverse events (AEs) will be coded using MedDRA. Common Terminology Criteria for Adverse Events (CTCAE) will be used to grade the severity of AEs. Treatment-emergent adverse events (TEAEs) are defined as AEs that start either on or after the first dose of the study drug and until first dose in study TV48574-IMM-20038 (if enrolled) or end of the FU period of the current study.

An overview table summarizing the following AE categories will be presented:

- Participants with at least 1 TEAE
- Participants with at least 1 TEAE CTCAE grade 3/4
- Participants with at least 1 treatment-related TEAE (related to IMP)
- Participants with at least 1 device-related TEAE
- Participants with at least 1 treatment-related TEAE CTCAE grade 3/4
- Participants with at least 1 serious TEAE
- Participants with at least 1 serious IMP related TEAE

- Participants with at least 1 serious device related TEAE
- Participants with at least 1 TEAE leading to discontinuation from the trial
- Participants with at least 1 TEAE leading to dose interruption
- Participants with at least 1 TEAE leading to treatment discontinuation
- Participants who died
- Participants with at least 1 protocol-defined TEAE of special interest (AESI)

Summaries will be presented for all TEAEs, and for the TEAE categories listed above.

The incidence of TEAEs will be summarized (overall and by grade) using descriptive statistics by SOC and PT (all TEAEs overall will also be presented by PT category in descending order of incidence in the pooled TEV-48574 group). Participants are counted only once in each SOC category, and only once in each PT category. For the summaries by grade, participants are counted at the highest grade. TEAEs that are missing information on seriousness will be excluded from the summary of serious TEAEs but included in the summary of non-serious TEAEs.

A Beta-binomial analysis of the 4 types of AEs used to define the stopping criteria in the interim safety analyses (see Section 13.1 and [Appendix 1](#)) will be conducted using the final data. The posterior probability that the AE rate in each active group and the 3 dose levels combined is larger than the AE rate in the placebo group will be reported for UC and CD separately and across the entire trial population.

Participant listings of all AEs, serious AEs, serious IMP related AEs, serious device related AEs, adverse events leading to discontinuation from the trial, and protocol-defined AESIs will be presented.

If any participant dies during the trial, a listing of deaths will be provided, and all relevant information will be discussed in the participant narrative included in the CSR.

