MMS	modified Mayo Score
(MM) SES-CD	modified multiplier Simple Endoscopic Score for Crohn's Disease
NRS	numerical response scale
[REDACTED]	[REDACTED]
PD	Pharmacodynamic
PK	Pharmacokinetic
PRO2	2-item patient-reported outcome

Abbreviation	Term
PT	preferred term
Q2W	every 2 weeks
R&D	Research and Development
RTSM	Randomization and Trial Supply Management
RNA	ribonucleic acid
S1P	sphingosine-1-phosphate
SAP	Statistical Analysis Plan
sc	subcutaneous
SD	Standard Deviation
SE	Standard Error
SES-CD	Simple Endoscopic Score for Crohn's Disease
SI	standard international
SOC	system organ class
SOP	standard operating procedure
TL1A	tumor necrosis factor (ligand) 1A
TNF- α	tumor necrosis factor-alpha
UC	Ulcerative Colitis
ULN	upper limit of normal
WHO	World Health Organization

INTRODUCTION

This Statistical Analysis Plan (SAP) describes the planned analysis and reporting for Teva Branded Pharmaceutical Products R&D, Inc. study TV48574-IMM-20036, (A 14-Week Phase 2b, RandomizEd, Double-BLInd, Dose-Ranging Study to Determine the Pharmacokinetics, Efficacy, Safety, and Tolerability of TEV-48574 in Adult PatiEnts with Moderate to Severe Ulcerative Colitis or Crohn's Disease (RELIEVE UCCD)), and was written in accordance with SOP GSD_RD_702 (Statistical Analysis Plan).

The reader of this SAP is encouraged to read the study protocol for details on the conduct of this trial, the operational aspects of clinical assessments, and the timing for completing the participation of a participant in this trial.

The SAP is intended to be in agreement with the protocol, especially with regards to the primary and all secondary endpoints and their respective analyses. However, the SAP may contain more details regarding these particular points of interest, or other types of analyses (e.g., other endpoints). When differences exist in descriptions or explanations provided in the study protocol and this Statistical Analysis Plan, the Statistical Analysis Plan prevails; the differences will be explained in the Clinical Study Report (CSR).

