2.1. General Design

This is a Phase 2b, randomized, double-blind, dose-ranging trial to determine the pharmacokinetics, efficacy, safety, and tolerability of TEV-48574 in adult participants with moderate to severe UC or CD. The trial will enroll adult participants (18 to 75 years of age, inclusive) of male and female sex (without restrictions on gender) with moderate to severe active UC or CD and who have demonstrated an inadequate response to, loss of response to, or intolerance to at least 1 of the following therapies: corticosteroids, immunosuppressant, or an advanced therapy for IBD including biologics, (anti-TNF, anti-integrins, anti-IL-12/23 or anti-IL-23), Janus kinase (JAK) inhibitors, or sphingosine-1-phosphate (S1P) receptor modulators, and no more than 3 locally approved classes of biologics (see protocol section 4.1 for definitions of these terms).

The trial will consist of a screening period of up to 6 weeks (42 days), a 14-week treatment period, and a 4-week follow-up period.

Screening: After providing written informed consent, participants will be screened within 6 weeks (42 days) prior to randomization to confirm that they have met all the selection criteria for the trial. At least 2 visits to the investigational site will be necessary to complete all screening procedures, including an endoscopy. The endoscopy should be performed after key eligibility criteria have been met and within approximately 10 calendar days of randomization (day 1) to allow for central endoscopy scoring.

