2.5. Sample Size and Power Considerations

A total trial sample size of approximately 240 participants is planned, with 120 participants (40 participants per dose arm) each for the 2 indications of UC and CD.

The sample size does not include participants that were randomized to the 1800 mg Q2W treatment group prior to Protocol Amendment 03 with Revision 01.

Assumptions:

The clinical remission and endoscopic response rates assumed in the sample size and related operating characteristics computations are as follows:

- Clinical remission rates in UC group: 8% for placebo; 30% for TEV-48574 groups, respectively
- Endoscopic response rates in CD group: 12% for placebo; 34% for TEV-48574 groups, respectively

Additional scenarios for remission (UC), response rates (CD) are assumed as outlined in [Table 2](#) to investigate the operating characteristics.

Table 2: Remission (UC), Response (CD) Rates Scenarios for Clinical Trial Simulations

Scenario	Indication	Placebo (%)	TEV-48574 450 mg Q2W (%)	TEV-48574 900 mg Q2W (%)
Null	UC	8	8	8
	CD	12	12	12

Table 2: Remission (UC), Response (CD) Rates Scenarios for Clinical Trial Simulations (Continued)

Scenario	Indication	Placebo (%)	TEV-48574 450 mg Q2W (%)	TEV-48574 900 mg Q2W (%)
Intermediate Efficacy	UC	8	20	20
	CD	12	25	25
Efficacy	UC	8	30	30
	CD	12	34	34
Efficacy-high dose only	UC	8	8	30
	CD	12	12	34

CD=Crohn's disease; Q2W=every 2 weeks; UC=ulcerative colitis.

Operating Characteristics:

Simulation-based operating characteristics for the analysis of the primary efficacy variable using a Bayesian Beta Binomial model are presented in [Table 3](#). This model uses a posterior probability cutoff of ≥ 0.90 to declare success at the final analysis.

Table 3: Operating Characteristics of Final Analysis

	UC			CD		
	TEV-48574 450 mg Q2W	TEV-48574 900 mg Q2W	At least 1 dose	TEV-48574 450 mg Q2W	TEV-48574 900 mg Q2W	At least 1 dose
Null	7.9%	7.9%	13.5%	9.6%	9.6%	16.1%
Intermediate efficacy	61.1%	61.1%	77.3%	59.3%	59.3%	75.9%
Efficacy	91.0%	91.0%	97.6%	87.1%	87.3%	95.5%
Efficacy-high dose only	7.9%	91.1%	91.1%	9.6%	87.2%	87.3%

CD=Crohn's disease; Q2W=every 2 weeks; UC=ulcerative colitis.

Beta-Binomial model with non-informative prior Beta(1,1); decision rule for declaring difference from placebo is based on having a posterior probability of ≥ 0.90 .

Note: Operating characteristics based on 500,000 simulations.

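### The TEAE definition in SAP Section 8.3 uses start date only, so a screening-onset AE kept as one record that worsens on drug is left out of the TEAE tables

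*SAP*

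**What the plan says.** Section 8.3 of the SAP sets the entry rule: "Treatment-emergent adverse events (TEAEs) are defined as AEs that start either on or after the first dose of the study drug". The window closes at the first dose in the extension study or at the end of follow-up. The section then lists the overview rows, all but one of which are worded as TEAEs; the exception is the row for deaths. Incidence by SOC and PT, overall and by grade, is also of TEAEs. The grade rule reads: "For the summaries by grade, participants are counted at the highest grade".

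Pre-dose safety data are kept but placed elsewhere. Section 8.1 says: "Safety listings will include all data collected, starting from screening". Section 8.3 also promises listings, beginning: "Participant listings of all AEs, serious AEs, serious IMP related AEs". Section 2.1 allows up to 42 days of screening.

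The SAP does not say whether a worsening AE is continued as the same record or entered as a new one.

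**The concern.** An AE that is already open at the first dose and becomes more severe or serious afterwards may be a drug effect. Readers compare arms using the TEAE tables, and in particular the serious and grade 3/4 rows. Under a test based on start date alone, such an event need not appear in those tables. Listings would show it participant by participant, but they do not give incidence by arm.

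The SAP does allow for worsening from an abnormal starting point in other safety data. In Section 10, a participant who is ADA-positive at baseline counts as treatment-emergent after at least a 4-fold rise in titer. In Table 6, several chemistry tests have a separate criterion when the baseline value is already abnormal. The AE definition has no counterpart to these rules.

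**Working it through.** The SAP gives no figure on this point and no arithmetic applies. The check follows one hypothetical event through the rules.

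1. **Can an AE be open at first dose?** Yes. Screening runs for up to 42 days (Section 2.1), and the safety listings cover data from screening onwards (Section 8.1).
2. **Does it meet the TEAE definition after worsening?** Suppose it starts in screening, stays one record, and reaches grade 3 or becomes serious after first dose. Its start date still precedes dosing, so it fails the Section 8.3 test whatever its later grade or seriousness.
3. **Does another rule bring it back?**
   - The highest-grade rule does not. It assigns a grade within the TEAE summaries and does not admit an AE that is not a TEAE.
   - The general rule in Section 8.1 does not. It describes treatment-emergent data as data collected from the first day of drug, which is looser, but it yields to more specific rules, and Section 8.3 is the specific rule for AEs.
   - A search of the remaining sections finds no clause on worsening, change of severity or splitting of AE records.
4. **Where is it lost?** From the overview rows, 12 of 13 of which are restricted to TEAEs, and from the SOC/PT and by-grade tables.
5. **Where does it still appear?**
   - In the listings of all AEs and, where applicable, of serious AEs and of AEs leading to discontinuation from the trial (Section 8.3).
   - If it has a measurable counterpart, in the laboratory shift and potentially-clinically-significant tables (Section 8.4), the liver tables (8.4.1), or the vital-sign and ECG summaries (8.5 and 8.6).
   - If it leads to withdrawal from the trial, in the Section 9 count, which is not worded as TEAE.
   - If the participant dies, in the deaths row.
6. **What remains uncovered?** Mainly clinical AEs that worsen or become serious on drug without a laboratory, vital-sign or ECG counterpart and without withdrawal or death. These have no place in any summary table.
7. **What if worsening is entered as a new AE?** The new record starts after first dose, meets the definition as written, and nothing is lost.

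**The case against.** The strongest objection is that the loss depends on a recording rule that cannot be seen here. Whether worsening opens a new AE record is commonly settled in the protocol or the CRF instructions. If it does, Section 8.3 works as written. This stands, and it makes the point conditional: the SAP wording permits an omission, but it does not show that one will occur.

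The Introduction says: "When differences exist in descriptions or explanations provided in the study protocol and this Statistical Analysis Plan, the Statistical Analysis Plan prevails". This has limited force. A protocol rule on splitting records would not conflict with Section 8.3; it would supply the start date that Section 8.3 uses. The clause matters only if the protocol defines TEAEs with a worsening clause, in which case the narrower SAP definition would override it.

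A second objection is that the fix adds little. With split records it is not needed, and with one record and no dated grade the grade part cannot be applied. This is partly right. The clause helps where a single record carries a dated grade change or a date on which it became serious, and the SAP does not say whether such fields exist.

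Two stronger readings are tempting, and the documents support neither:

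- *Such events would be visible only in listings.* Step 5 of the working shows other routes for some of them.
- *The final Bayesian safety comparison would be distorted.* Section 8.3 plans: "A Beta-binomial analysis of the 4 types of AEs used to define the stopping criteria in the interim safety analyses". That sentence refers to AEs, and the SAP does not say whether the set is limited to TEAEs. The analysis reports a probability, while the cutoffs belong to the interim rules. The start-date rule applies to placebo as well as active arms, so an omitted event could move a comparison either way. Any numerical example would rest on invented counts and would not measure the gap.

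**Conclusion.** The point holds in conditional form. As written, Section 8.3 leaves out of the TEAE rows and tables any AE that starts before first dose, is kept as one record, and worsens in CTCAE grade or becomes serious on drug. This follows from the wording of the definition and needs no assumption about rates or sample size.

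The number of such events cannot be estimated from the SAP, and the direction of any effect on arm comparisons is unknown. There is no effect if worsening is recorded as a new AE. A reader might infer that Section 8.1, Section 8.3 and Section 9 contradict one another. They do not: 8.1 gives way to the specific AE rule, and Section 9 counts withdrawals on its own terms. The change is a worthwhile low-cost improvement rather than a necessary correction.

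**What to change.** In Section 8.3, extend the definition so that TEAEs are AEs that start on or after the first dose, *or that start before the first dose and worsen in CTCAE grade or become serious on or after it*. Keep the existing end of the window. Add that such events are counted at their highest on-treatment grade.

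If the recording rules already enter worsening as a new AE with its own start date, one sentence in Section 8.3 saying so is enough.

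The cost is one or two sentences and no new data collection. A few more events will need review. The clause can be applied only where there is a dated grade change, a split record or a dated change to serious.
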